#### Exclusion Criteria

- Receiving vancomycin monotherapy or oral broad-spectrum antibiotics
- Inability to receive oral fluids
- Self-reported allergy or intolerance to any ingredients in NBT-NM108
- Surgery involving the intestinal lumen within the last 30 days
- Documented diagnosis of celiac disease, inflammatory bowel disease or irritable bowel syndrome
- Pregnancy or breastfeeding
- Bariatric surgery
- Immunocompromised, e.g., cancer treatment, bone marrow/organ transplant, immune deficiency, poorly controlled HIV/AIDS, prolonged use of steroids or other immunosuppressant medications

#### 4.2 Secondary Subjects

Not applicable

#### 4.3 Number of Subjects

## A. Total Number of Subjects

100

# **B. Total Number of Subjects If Multicenter Study**

N/A

# C. Feasibility

There are over 2,000 new COVID-19 cases every day in Florida. Around 100 individuals attend the USF Carol & Frank Morsani Center for Advanced Healthcare drive-through testing center for COVID-19 testing each day and among the confirmed cases the prevalence of diabetes is 12%. We therefore consider this patient flow sufficient for recruiting the targeted number of subjects in the specified duration.

#### 4.4 Consent Procedures

#### A. Consent Process

Location of Consent Process

Protocol Title: COVGUT20

The electronic consent process will take place during virtual interviews on eConsent, a video call module from the cloud-based clinical data management platform Castor. Individuals who are willing to participate in this study will provide their electronic informed consent during the interview.

## Ongoing Consent

Not applicable

## Individual Roles for Researchers Involved in Consent

Study coordinators will conduct the consent interview to explain all aspects of the study and answer any questions the prospective participants may have.

#### Consent Discussion Duration

The consent discussion will take approximately 30 min.

#### Coercion or Undue Influence

In order to minimize the possibility of coercion or undue influence, the consent process will not be conducted by research personnel who have financial conflicts of interest or any known relationship or conflict of interest with the prospective participants.

#### Subject Understanding

Throughout the consent process the prospective participants will be encouraged to ask any questions should they feel the need to do so. The consent process will be divided into a series of small sections. Members of the research team will summarize each section, use probe questions to check for sufficient understanding before proceeding to the next section.

#### B. Waiver or Alteration of Consent Process

# Waiver or Alteration Details

We are requesting an alteration of the consent process. Prospective participants will be provided with a copy of the consent form (Appendix 3) prior to a virtual consent interview on eConsent, a video call module of the cloud-based clinical data management platform Castor. During this interview, the study coordinator will go through the contents of the consent form with the prospective participants and both parties will provide electronic signatures on the consent form (Appendix 4) if the prospective participants are willing to provide information for eligibility screening. This alteration aims to minimize face-to-face contact between research personnel and COVID-19 patients.

#### Destruction of Identifiers

The master code identifier, which contains personal information of subjects and the participant code assigned to them, will be deleted from the server 6 years after study completion.

#### Use of Deception/Concealment

Not applicable

#### C. Documentation of Consent

#### Documenting Consent

Prospective participants and the study coordinator who conducts the consent process will view and provide electronic signatures on the consent form in real-time on Castor, and both parties will keep a copy of the form.

# Waiver of Documentation Of Consent (i.e., will not obtain subject's signature) Not applicable

# 4.5 Special Consent/Populations

#### A. Minors-Subjects Who Are Not Yet Adults

Not applicable

Protocol Title: COVGUT20

#### B. Wards of the State

Not applicable

## C. Non-English-Speaking Subjects

Not applicable

## D. Adults Unable to Consent / Decisionally Impaired Adults

Not applicable

## 4.6 Economic Burden and/or Compensation for Subjects

#### A. Expenses

We do not expect any expenses the participants will incur by taking part in the research.

#### B. Compensation/Incentives

Participants will receive compensation of up to \$100.00, which will be paid in the form of a USF ClinCard if they are recruited from the USF COVID testing center or in the form of reward cards if they are recruited online. The stipend will be available to the participants within one week after they successfully reach the following milestones:

- \$25.00 after the completion of sample collection and shipment at Day 0
- \$25.00 after the completion of sample collection and shipment at Day 28
- \$25.00 after the completion of sample collection and shipment at Day 56, and an additional \$25.00 if the participants successfully complete sample collection and shipment at all time points (including sample collection and shipment at the day of recovery, if applicable)

## C. Compensation Documentation

Not applicable

#### 4.7 Risks of Harm/Potential for Benefits to Subjects

#### A. Description of Risks of Harm to Subjects

# Reasonably Foreseeable Risks of Harm

Measuring fasting blood glucose during the study both involve a finger prick that pierces the skin. There may be a bruise, bleeding, or infection, at the place where the skin is pierced. However, infection is rare. Collecting fecal samples at home may impose inconvenience for the participants and their families. Participants may experience gastrointestinal symptoms (e.g. abdominal pain/discomfort, constipation, or bloating). These discomforts are minor and should not last longer than a few hours. Participants in the treatment group may experience hypoglycemia when they take NBT-NM108 if they are on diabetic medications. This product is low in digestible and simple carbohydrates and may reduce food intake. For participants who are already on diabetic medications (insulin and/or oral hypoglycemic agents) which lower blood glucose, the medication may reduce blood glucose beyond its normal level.

# Risk of Harm from an Intervention on a Subject with an Existing Condition

Not applicable

#### Other Foreseeable Risks of Harm

Not applicable

#### Observation and Sensitive Information

Not applicable

## B. Procedures which Risk Harm to Embryo, Fetus, and/or Pregnant Subjects

Not applicable

#### C. Risks of Harm to Non-Subjects

Protocol Title: COVGUT20

Fecal sample collection at home may impose inconvenience for individuals in the same household.

# D. Assessment of Social Behavior Considerations

Not applicable

# E. Minimizing Risks of Harm

Participants will be provided with oral and written instructions and supplies to collect fecal samples at home without direct physical contact with the specimens throughout the process. The specimens will be stored in a sealed container, a leak-proof secondary package (a sealable plastic bag lined with absorbent pads) and an outer package (e.g. a shipping box). Participants are not required to store the samples at home; they will mail the specimens to the research team using the shipping supplies provided.

To minimize adverse effects due to NBT-NM108, participants in the treatment group will be asked to gradually increase the dose to avoid adverse events associated with an acute increase in fiber intake. They will also be advised to drink enough fluids throughout the study including the amount of water taken together with NBT-NM108) to avoid constipation. Participants will be asked to monitor potential adverse events daily. If participants report an adverse event, a member of the study team will contact them to ask follow-up questions about the degree of severity (mild, moderate, or severe) and the frequency of the adverse events. The study physician (co-PI [name]) will assess the adverse events and, if necessary, she will instruct the participants to reduce the consumption of NBT-NM108 to a lower dose that has been tolerated, and so on. If the same level of discomfort continues i.e.. for three consecutive days, the treatment will be discontinued. Participants are also at asked to closely monitor their blood glucose level and discuss with their family physicians about adjusting their medications to prevent hypoglycemia.

To monitor COVID-19-like symptoms, participants will evaluate their symptoms and report to the research team on Castor twice a day from Day 1 to Day 28 or until they recover from COVID-19-like illness (whichever is later) and once a week thereafter until Day 56 (i.e. the mornings of Days 35, 42, 49 and 56 as appropriate). For those who are hospitalized during the study, after they are discharged they will also be asked to evaluate their symptoms and report to the research team on Castor twice a day until they recover from COVID-19-like illness and once a week thereafter until Day 56. The study team will review the symptom diary within 24 h of each entry and follow up with the participants if the symptoms require medical attention. The study team will call all participants at least once a week to monitor their progress. Participants are also instructed to call 911 if they notice any of the following red flags: respiratory rate  $\geq$  30/min, pulse rate  $\geq$  125/min, oxygen saturation level  $\leq$  93%, severe shortness of breath at rest (inability to talk in full sentences), difficulty breathing, persistent pain/pressure in chest, cold/clammy/pale/mottled skin, new confusion or inability to wake up, blue lips or face, little or no urine output or hemoptysis. Participants with T2DM will be instructed to call the physician who normally manages their diabetes if their fasting blood glucose is < 60 mg/dL or > 300 mg/dL.

# Certificate of Confidentiality

Not applicable

# Provisions to Protect the Privacy Interests of Subjects

Should any participants desire not to interact with or provide personal information to specific members of the research team, they may report such a need to the PI and the arrangement of the research personnel will be adjusted accordingly. Participants will not be required to provide a reason if they desire not to do so. Should changing of the research personnel is not possible, the PI will discuss with the subjects about alternative solutions.

Each participant will be assigned a unique identification code. A master code identifier which links the identification code and personal information will be maintained separately from the study data. Subject information and de-identified study data are only accessible to named investigators in this protocol and authorized research personnel. All data and materials collected during this study are for research

Protocol Title: COVGUT20

purpose only, and the data will be kept in strict confidence. No information will be given to anyone without permission from the subjects.

# F. Potential Benefits to Subjects

Participants in the treatment group may have reduced severity of COVID-19-related illness.

## 5.0 Special Considerations

#### 5.1 Health Insurance Portability and Accountability Act (HIPAA)

We will ask participants for their consent so that designated members of the research team can review his/her medical record to retrieve medical history, medications, clinical and laboratory data related to COVID-19-like illness. All received health information will be stored in a password-protected file which is stored on the university's secure server and will only be accessible to authorized research personnel.

# 5.2 Family Educational Rights and Privacy Act (FERPA)

Not applicable

# 5.3 Code of Federal Regulations Title 45 Part 46 (Vulnerable Populations)

#### A. Special Populations

Not applicable

## 5.4 General Data Protection Regulation (GDPR)

Not applicable

# 5.5 NJ Access to Medical Research Act (Surrogate Consent)

Not applicable

#### 6.0 Data Management Plan

#### 6.1 Data Analysis

DNA, protein, and metabolites will be extracted from fecal samples. 16S rRNA gene V4 region sequencing and metagenomic shotgun sequencing with different platforms such as Ilumina and PacBio will be done using the extracted DNA. Metaproteome profiling will be achieved using mass spectrometry-based proteome analysis based on extracted protein. Metabolomics will be measured using fecal sample supernatant. Multiomics data will be combined with clinical data for statistical analysis to explore the overall changes during COVID-19 course and changes induced by the treatment.

16S rRNA gene sequencing data will be analyzed based on the amplicon sequence variants (ASVs) [28] to determine the gut microbiota composition using QIIME 2 [29]. Shannon index and ASV richness will be used to assess alpha diversity. Principal coordinate analysis will be used to compare and visualize dissimilarity in gut microbiota structure between samples based on beta diversity (Weighted and Unweighted UniFrac distance) and statistical differences will be tested using permutational multivariate analysis of variance (PERMANOVA). PICRUSt 2 will be used to predict the functions of individual ASVs and the collective functions of the gut microbiota at the gene content and pathway levels [30]. Global functional profiles of the gut microbiota will be compared and visualized by principal component analysis.

Metagenomic sequencing data will be analyzed in a genome-centric way. The raw sequencing data will be processed with KneadData (https://huttenhower.sph.harvard.edu/kneaddata) for quality control. High quality draft genomes will be de novo assembled from the high-quality sequencing data. The quality assessment, taxonomic assignment and functional annotation of the genomes will be conducted by using CheckM [31], GTDB-Tk [32] and Prokka [33] respectively. Principal coordinate analysis will be used to compare and visualize dissimilarity in gut microbiota structure between samples based on beta diversity and statistical differences will be tested using permutational multivariate analysis of variance (PERMANOVA).

Protocol Title: COVGUT20

The metaproteomes will be analyzed by using Unified Human Gastrointestinal Genome (UHGG) v2.0 as the reference for functional annotation and protein sequences database. The predicted protein sequences from metagenomic dataset will be aligned with the measured protein sequences from metaproteomic dataset for integrative analysis. Global level protein changes of the gut microbiota will be compared and visualized by principal component analysis. The metabolome will measure both polar metabolites and lipids. Global level of compound changes of will be compared and visualized by principal component analysis.

Repeat measures correlation will be used to assess the relationships between ASVs/high quality draft genomes [34], followed by ASV/high quality draft genome clustering based on co-abundance patterns. Multivariate methods such as MaAsLin2, that allow adjustment for confounding variables and model the covariates as random effects, will be applied to interpret the relationship between ASVs / ASV co-abundance groups/functions/high quality draft genomes/high quality draft genome co-abundance groups and the clinical metadata/proteins/metabolites.

To analyze the clinical data, Aalen's additive survival model will be used to test whether the impact of covarites on the cumulative hazard is time-dependent [35]. If the covariates do not vary with time, cox proportional hazards model will be subsequently used to adjust for age, gender, race/ethnicity, baseline COVID-19 severity, and whether the participant has taken treatments that may reduce COVID-19 severity (vaccination and monoclonal antibody treatment) as covariates. Survival analysis Kaplan-Meyer curves and log-rank test will be used to estimate and compare the risk of death and the risk of recovery, as a function of time, in participants with COVID-19-like symptoms [36, 37]. To compare the time to hospitalization, the time to recovery, the time to complete resolution of subjective symptoms, and the time to complete resolution of objective symptoms between treatment groups, we will use competing risks survival analysis (treating death or self-reported illness severity at Days 1, 14, 28 and 56 as a competing risk) [36, 38], use survival analysis without competing risk, and explore joint survival analysis and Bayesian survival model [39]. Specifically, cumulative incidence functions will be estimated and tested using Gray's test [40]. The Fine-and-Gray subdistribution hazard regression analysis [38] will be used to further adjust for age, gender, race/ethnicity, baseline COVID-19 severity, and whether the participant has taken treatments that may reduce COVID-19 severity (vaccination and monoclonal antibody treatment) as covariates. Proportion of participants who are "alive and not admitted to the hospital", proportions of participants who visit the emergency room at Days 1, 14, 28 and 56, have complete resolution of objective symptoms, have complete resolution of subjective symptoms and have complete resolution of subjective symptoms except cough and fatigue at Days 1, 14, 28 and 56 will be compared between groups using separate logistic regression analysis at each time point. Time for participants to have complete resolution of objective symptoms, complete resolution of subjective symptoms and complete resolution of subjective symptoms except cough and fatigue will be compared between groups using competing risks survival analysis described previously, treating death or self-reported illness severity at Days 1, 14, 28 and 56 as a competing risk [36, 38]. To compare the longitudinally (repeatedly) measured illness severity based on the Ordinal Scale for Clinical Improvement from the World Health Organization, body temperature (oral), oxygen saturation level, pulse rate, respiratory rate and fasting blood glucose between treatment groups, accounting for the effect of death, reported adverse event, or other appropirate competing risk, we will compare the treatment effect using the method of joint survival and longitudinal data analysis [41, 42], where each of the clinical outcomes (e.g., illness severity, body temperature (oral), and oxygen saturation level, etc.) will be modeled using linear mixed models, and death, reported adverse event, or other appropirate competing risk will be modelled using Weibull proportional hazards model [43]. Age, gender, race/ethnicity, baseline COVID-19 severity, and whether the participant has taken treatments that may reduce COVID-19 severity (vaccination and monoclonal antibody treatment) will be controlled as covariates in these statistical analyses, where appropriate. Within-group changes of main outcomes between groups will be modeled as change from pre- to post-treatment using ANOVA and modeled as the post-treatment value as the change itself with the pretreatment value entered as covariate using ANCOVA [44]. Lastly, alternative statistical methods will be explored to quantify the underlying differences between groups with respect to a time-to-event end point, robust methods include calculating ratio/difference of t-Year Survival Rates, ratio/difference of percentiles of survival functions, and ratio/differenceof restricted mean survival times or restricted mean time lost [45]. Statistical analyses described above will be conducted for both intent-to-treat dataset and per-protocal dataset. For each test of an outcome, we define the statistical significance by p<0.05. The false discovery rate [46] will be applied for multiple testing, where appropriate. Sensitivity analysis using multiple imputation methods [47] will be performed to handle the missing data. Other

approaches, such as methods of selection models [48] or use the pattern-mixture models such as the controlbased pattern imputation approach, or the tipping-point approach [49, 50] will also be considered.

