## **B.** Data Points

- Gut microbiota composition: fecal samples will be collected at Days 0, 28, 56 and the day when participants recover from COVID-19-like illness (if before Day 56)
- Clinical progress of COVID-19-like illness: 1) objective and subjective symptoms data will be collected twice a day from Day 1 to Day 28 or until they recover from COVID-19-like illness (whichever is later) and once a week thereafter until Day 56 (i.e. in the mornings of Days 35, 42, 49 and 56); and 2) COVID-19-like illness severity will be assessed at Days 1, 14, 28 and 56 using the categorization from FDA [18] and the Ordinal Scale for Clinical Improvement from the World Health Organization [19]
- Proportion of participants who are "alive and not admitted to the hospital" at Days 1, 14, 28 and 56
- Proportion of participants who visit the emergency room at Days 1, 14, 28 and 56
- Outcome of COVID-19-like illness (hospitalization or death) at Days 1, 14, 28 and 56
- Glucose homeostasis if the participant has T2DM: fasting blood glucose will be measured in the mornings from Day 1 to Day 28 or until they recover from COVID-19-like illness (whichever is later) and weekly thereafter until Day 56

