## D. Endpoints

- 1. Primary outcome:
  - Gut microbiota composition
- 2. Secondary outcomes:
  - At Days 1, 14, 28 and 56:
  - a) Outcome of COVID-19-like illness (hospitalization or death)
  - b) Proportion of participants who are "alive and not admitted to the hospital"
  - c) Proportion of participants who visit the emergency room
  - d) Proportion of participants who have complete resolution of all objective symptoms, i.e. all vital signs are within the normal range for at least 48 h, including body temperature (oral) 36.5-37.5°C (97.7-99.5°F), pulse rate 60-100/min, respiratory rate 12-20/min and oxygen saturation level at 95-100%
  - e) Proportion of participants who have complete resolution of subjective symptoms, i.e. absence of all COVID-19-like symptoms listed by CDC (updated May 13, 2020) for at least 48 h, including the presence of chills or "feeling feverish", cough, shortness of breath or difficulty breathing, fatigue, muscle or body aches, headache, new loss of taste or smell, sore throat, congestion or runny nose, nausea or vomiting and diarrhea
  - f) Proportion of participants who have complete resolution of subjective symptoms except fatigue and cough, i.e. absence of all COVID-19-like symptoms listed by CDC (updated May 13, 2020) for at least 48 h, including the presence of chills or "feeling feverish", cough, shortness of breath or difficulty breathing, fatigue, muscle or body aches, headache, new loss of taste or smell, sore throat, congestion or runny nose, nausea or vomiting and diarrhea
  - g) Illness severity based on the categorization from FDA [18] and the Ordinal Scale for Clinical Improvement from the World Health Organization [19]
  - h) Body temperature (oral)
  - i) Oxygen saturation level
  - i) Pulse rate
  - k) Respiratory rate
  - I) Fasting blood glucose
  - Time to complete resolution of all objective symptoms
  - Time to complete resolution of all subjective symptoms
  - Time to complete resolution of all subjective symptoms except fatigue and cough

Protocol Title: COVGUT20

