## 1.5 Sample Size Justification

We will enroll a total of 100 participants who have COVID-19-like symptoms and have positive/pending PCR-based COVID-19 test results. These individuals will be randomized into the control and treatment group in a 1:1 ratio (i.e. 50 participants/group). With the assumption of a positivity rate of 40-50% in symptomatic participants in the USF Carol & Frank Morsani Center for Advanced Healthcare drive-through testing center, we expect to have at least 20 confirmed COVID-19 cases in each group. We used the micropower R-package [27], in which the weighted Jaccard distance matrix was simulated based on within-group distance variance (mean and standard deviation) of data from 36 T2DM patients (unpublished data) to estimate the required sample size. Using the simulated matrices, the PERMANOVA powers are calculated for varying effect sizes ( $\omega^2$ ) and sample sizes. Our results show that 16 subjects per group afford 80% power to an  $\omega^2$  of 0.0106 which correspond to the difference ( $\omega^2$ =0.0120) between the control and treatment group with a similar high-fiber intervention in the T2DM patients (unpublished data). We therefore aim to recruit 20 confirmed COVID-19 cases in each group to allow for potential dropouts and/or incomplete sample/data sets from the participants.

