Metagenomic sequencing data will be analyzed in a genome-centric way. The raw sequencing data will be processed with KneadData (https://huttenhower.sph.harvard.edu/kneaddata) for quality control. High-quality draft genomes will be de novo assembled from the high-quality sequencing data. The quality assessment, taxonomic assignment, and functional annotation of the genomes will be conducted by using CheckM [4], GTDB-Tk [5], and Prokka [6] respectively. The principal coordinate analysis will be used to compare and visualize dissimilarity in gut microbiota structure between samples based on beta diversity, and statistical differences will be tested using permutational multivariate analysis of variance (PERMANOVA).

The metaproteomes will be analyzed by using Unified Human Gastrointestinal Genome (UHGG) v2.0 as the reference for functional annotation and protein sequences database. The predicted protein sequences from metagenomic dataset will be aligned with the measured protein sequences from metaproteomic dataset for integrative analysis. Global level protein changes of the gut microbiota will be compared and visualized by principal component analysis. The metabolome will measure both polar metabolites and lipids. Global level of compound changes of will be compared and visualized by principal component analysis.

Repeat measures correlation will be used to assess the relationships between ASVs/highquality draft genomes [7], followed by ASV/high-quality draft genome clustering based on co-abundance patterns. Multivariate methods such as MaAsLin2, that allow adjustment for confounding variables and model the covariates as random effects, will be applied to interpret the relationship between ASVs / ASV co-abundance groups/functions/high-quality draft genome co-abundance groups and the clinical metadata/proteins/metabolites.

Clinical Data Analysis

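### The primary outcome has no named primary test, and the plan does not clearly commit to a multiplicity correction for the several microbiome tests it describes

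*Protocol*

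**What the plan says.** Protocol section 1.3 D lists one primary outcome, "Gut microbiota composition", and stops there. The main group of secondary outcomes in the same list is tied to Days 1, 14, 28 and 56, and several have numerical criteria.

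Section 1.3 B sets the sampling: "fecal samples will be collected at Days 0, 28, 56 and the day when participants recover from COVID-19-like illness (if before Day 56"). Under section 1.3 A the product is taken from Day 1 to Day 28, so Day 28 is the end of dosing and Day 56 is 28 days later.

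Section 6.1 describes two sets of PERMANOVA tests:
- 16S data are compared "based on beta diversity (Weighted and Unweighted UniFrac distance) and statistical differences will be tested using permutational multivariate analysis of variance (PERMANOVA").
- Metagenomic data are compared "between samples based on beta diversity and statistical differences will be tested using permutational multivariate analysis of variance (PERMANOVA"), with no distance named.

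The SAP repeats both under Sequencing Data Analysis; the metagenomic sentence there reads "based on beta diversity, and statistical differences will be tested using permutational multivariate analysis of variance (PERMANOVA"). Shannon index and ASV richness are to describe alpha diversity.

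The significance rule comes at the end of section 6.1: "For each test of an outcome, we define the statistical significance by p<0.05". The next sentence cites an FDR method for dependent tests, to be used where it is judged appropriate, and gives no family and no level. The analyses are to be run on both the intent-to-treat and the per-protocol sets, neither named as primary. In the SAP these sentences fall under Clinical Data Analysis, and Sequencing Data Analysis has no multiplicity rule.

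The sample size (section 1.5) rests on another metric, "in which the weighted Jaccard distance matrix was simulated based on within-group distance variance (mean and standard deviation").

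**The concern.** A primary outcome should lead to one result that can be identified before the data are seen. Here the outcome is a concept, and the analysis text offers several routes to a p-value: two named UniFrac distances, an unnamed metagenomic distance, up to three post-baseline samples and two analysis sets. The routes answer different questions. Day 28 measures the effect at the end of dosing, Day 56 its persistence, and the recovery-day sample falls at a different time for each participant.

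Two things are at stake. If each result is read at p<0.05, an inert product has more than a 5% chance of producing a significant primary finding. A mixed pattern, such as unweighted UniFrac positive at Day 56 only, would also have no agreed interpretation. FDR control, even if applied, would not say which result was the planned primary one.

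**Working it through.** **The plan's own figure.** Section 1.5 gives 80% power with 16 per group at ω² = 0.0106. It cannot be recomputed, because the mean and standard deviation of the within-group distances come from unpublished data. It refers to a single PERMANOVA on weighted Jaccard, which is not one of the distances named for analysis. The documents state no family-wise error rate.

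**Counting the tests.** The documents do not say that PERMANOVA is run visit by visit. If it is:
- two UniFrac distances × Days 28 and 56 = 4 tests;
- two UniFrac distances × three samples = 6 tests;
- adding the metagenomic distance, three × three = 9 tests.

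**Independent tests.** The chance of at least one p<0.05 under the null is 1 − 0.95^k:
- k = 4: 1 − 0.8145 = 18.5%
- k = 6: 1 − 0.7351 = 26.5%
- k = 9: 1 − 0.6302 = 37.0%

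**Correlated tests.** The correlation is an assumption. Upper-tail normal test statistics were simulated (200,000 runs) with correlation r between distances and the same r between samples; tests differing in both have correlation r².

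| r | 4 tests | 6 tests | 9 tests |
|---|---|---|---|
| 0 | 18.7% | 26.5% | 37.0% |
| 0.3 | 17.0% | 23.2% | 31.1% |
| 0.5 | 15.0% | 19.9% | 25.9% |
| 0.7 | 12.6% | 15.9% | 19.8% |
| 0.9 | 9.2% | 10.7% | 12.2% |

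(At r = 0, four tests, the simulated 18.7% differs from the exact 18.5% only by simulation error.)

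**Direct PERMANOVA simulation under the null.** Two separate simulations, with taxa, within-person correlation and stand-in distances all assumed, gave at least one rejection as follows:
- 50 per arm: 22–27% for six tests and 24–31% for nine.
- 20 per arm (800 trials, 199 permutations): 22.9% for six and 23.9% for nine, with a Monte Carlo standard error of about 1.5 points for the latter.

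**If FDR were applied across all nine tests at 0.05.** With no true effect anywhere, the chance of any significant result is 2.9–5.0% with Benjamini-Hochberg. It is 1.0–1.8% with Benjamini-Yekutieli, the dependency method the plan cites.

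The result therefore turns on whether the FDR sentence covers these tests. In the protocol it closes a paragraph that opens with the clinical data, but section 6.1 has no subheading separating that paragraph from the sequencing text. In the SAP a heading does separate them. The documents do not settle the question.

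**The case against.** A reader might infer that the primary outcome is tested at least nine times without correction, and that an inert product therefore has a 1 in 4 chance of success. The documents do not support that.

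- **The FDR sentence directly follows the p<0.05 sentence.** Both sit in the same paragraph, so it is inconsistent to apply one to the microbiome tests and exclude the other. If both apply and the family covers these tests, the error is at most 5%. If neither applies, the plan states no significance level for its primary outcome.
- **Nine is not a minimum.** Only two distances are named, and section 6.1 links composition to the 16S data. The recovery-day sample exists only if recovery comes before Day 56. Testing at each visit is stated for the clinical proportions but not for PERMANOVA, so a repeated-measures or change analysis would also fit the text. Alpha diversity is to be assessed, with no test specified.
- **1 in 4 depends on assumed correlation.** The documents give nothing from which to estimate it.
- **The stated purpose is partly exploratory.** Section 1.1 speaks of feasibility and exploring relevance.

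The first three points stand and limit the claim to a conditional range. The fourth carries less weight: the objectives in the same section include effectiveness, section 1.5 claims 80% power for a PERMANOVA, and section 6.1 sets a significance threshold. None of the four supplies the missing primary test, and a conditional FDR sentence without a family does not commit the sponsor to any correction.

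**Conclusion.** The concern holds as a gap in specification with a conditional cost. Neither document names a primary distance, time point, data type, between-arm contrast or analysis set, and the reach of the FDR sentence is undefined. If about four to nine tests were read uncorrected, the chance of at least one false-positive primary result would be roughly 9% (four tests, r = 0.9) to 37% (nine independent tests), against 5% for one named test. For nine tests at moderate correlation (r = 0.5) it is 26%, about 1 in 4.

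These figures rest on three assumptions: per-visit testing, no FDR applied to these tests, and correlations between 0 and 0.9. They leave out the second analysis set and alpha diversity, which would add further tests. They do not show that the plan has a 1 in 4 error rate; they show that the text does not exclude one. The gap needs to be closed before the sequencing data are analysed.

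**What to change.** Amend protocol sections 1.3 D and 6.1 and the Sequencing Data Analysis section of the SAP to:

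1. Name one primary test: PERMANOVA on 16S data, Day 28 samples, treatment versus control, one sample per participant, intent-to-treat set, one stated distance. If both UniFrac distances are wanted, use a single permutation minimum-p test over the two at Day 28, which gives one p-value at the 5% level.
2. Make Day 56, the recovery-day sample, metagenomics, alpha diversity and the per-protocol set secondary, in one named FDR family with a stated level and method.
3. Reconcile the primary test with section 1.5, which uses weighted Jaccard and counts confirmed cases (20 sought per group out of 50 randomized). Either align the distance and population, or restate the power for the test chosen.

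The cost is wording, plus a new power statement if the distance or population changes. The sponsor gives up the option of calling a Day 56 or second-distance result the primary finding.
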